D.3.1.1 Rationale for Study Design. *Why Use a Waitlist Design?* We chose a waitlist control group as a usual care comparison group because PR intake evaluations are typically scheduled 6 weeks in advance of implementation. Therefore, 4-week CALM Breathing could fit seamlessly into PR programs and not delay standard of care. A qualitative study found that waiting for PR increased patients' feelings of uncertainty and lack of control regarding their care.¹⁸² Our experience shows that once referred to PR, patients are motivated to start some form of therapy right away. CALM Breathing can leverage patients' motivation and reduce feelings of uncertainty. A target sample size of 40 subjects is justified based on the primary outcomes of feasibility and acceptability, and transition of participants to a 10-week PR program.

D.3.1.2 Rationale for Study Need. This study is part of our phased approach to refine, optimize, and test the feasibility of CALM Breathing. Preliminary participant feedback from our CATCH study was applied to adapt and design CALM Breathing (including its dose, schedule, delivery, and home program). This pilot builds on initial lessons learned and identifies intervention areas still needing greater development to assure the success of a future large trial, targeting a subpopulation at risk, that is, those with COPD and anxiety.

The purpose of this pilot study is to establish success benchmarks of CALM Breathing and to test feasibility of:

- 1) recruiting a target group of adults with COPD and concurrent anxiety, including building a partnership with Columbia University Irving Medical Center's (CUIMC's) pulmonary department; ensuring adequacy of recruitment and study referral procedures;
- 2) using ASI-16, DMQ-CAT, and VAS dyspnea anxiety assessments for eligibility screening;
- 3) randomizing participants to CALM Breathing and Wait-List;

- assessment procedures; confirming our estimates of time needed to administer assessments; evaluating participant ratings of assessment burden; and testing that target timelines and blinding are achievable;¹⁸³
- 5) facilitating timely PR intake assessment initiation (to limit wait);
- 6) implementing manualized CALM Breathing, including adequacy of dose (timing, frequency, and session duration), fidelity procedures, and transportation funds; attention will be given to additional considerations and tailoring needs of patients with significant anxiety sensitivity and/or anxiety disorders;
- implementing home-based breathing exercise component (e.g., new RR device fidelity checks and new distribution of therapist-guided audio exercises using an MP3 player to improve adherence rate);^{181,184,185}
- 8) retaining participants at 3-month follow-up post-PR, including ensuring adequacy of retention strategies.

D.3.2 Participant Eligibility and Recruitment. Participants will be recruited from CUIMC's / New-York Presbyterian Hospital's outpatient PR program patient referral list. Participants will also be recruited from a cooperating clinical site, CUIMC's / New-York Presbyterian Hospital's Pulmonology Medicine Department, CUIMC'S/ New-York Presbyterian Hospital's Primary Care Medicine Department and New-York Presbyterian Lawrence Hospital Pulmonology Medicine Department. We will also plan to make use of CUIMC's RecruitMe platform. To facilitate participant recruitment and partnership building, we will partner with the [name], MD and [name], MD from CUIMC's/New-York Presbyterian Hospital's Pulmonology Medicine Department and [name] from CUIMC's/New-York Presbyterian Hospital's Primary Care Medicine Department. CUIMC has a high volume of racially diverse patients with COPD. Feasibility of conducting this study is facilitated by a single Institutional Review Board (IRB) and a single-clinic recruitment site.

D.3.2.1 *Inclusion Criteria*: Eligible participants will be adult males or females with COPD in stable condition; have elevated anxiety symptoms;^{57,186} have dyspnea symptoms; and require ≤8 hours per day of supplemental oxygen. All participants will receive standard care of pharmacotherapy with bronchodilators.^{77,12} Participants taking anti-anxiety medication (e.g., selective serotonin reuptake inhibitors, SSRIs, and serotonin norepinephrine reuptake inhibitors, SNRIs) must be stably medicated for at least 4 weeks prior to study entry,¹⁵² with no plans to change psychotropic medication dose.

D.3.2.2 *Exclusion Criteria*: Participants may not have suicidal ideation or suicidal behaviors within the past year (score of >1 on psychologist interview-administered Clinician Suicide Assessment Checklist, which is a Modified Columbia-Suicide Severity Rating Scale-CSSRS).¹⁸⁷ Participants cannot have morbid obesity (body mass index (BMI) > 40) or neuromuscular disease or be pregnant. Participants not eligible for CUIMC's PR program and those who have received PR training in past 12 months will be excluded. Concurrent receipt of short-term or new physical therapy, speech therapy, mindfulness, or meditation-based therapies (e.g., Mindfulness Based Stress Reduction) will not be permitted. Cognitive impairment will be screened by the Mini Mental State Exam, with score of ≤23 used as an exclusion criterion, to control for cognitive impairment and learning challenges.¹⁸⁸ [See Study Record for full eligibility criteria.]

D.3.2.3 Rationale for Eligibility Criteria. Assessments for elevated anxiety symptoms are based on our previous research.^{22,57,189} No diagnosis of an anxiety disorder is required since participants with elevated anxiety symptoms could benefit from CALM Breathing. An inclusion criteria of anxiety symptoms (rather than anxiety disorder) increases the generalizability and potential impact of CALM Breathing, targeting anxiety and somatic symptoms such as occur with breathing in COPD. We will use accepted standards of spirometry testing to classify COPD patients (using grades 1 to 4) according to severity of airflow limitation.¹² Neuromuscular disease can affect PaCO₂.³⁰ Obesity is associated with hypercapnia. Our threshold of hypercapnia of ETCO₂ > 50 mmHg is widely used.¹⁹⁰ Pregnancy can reduce ventilatory control, resulting in hyperventilation, hypocapnia, and alkalosis.¹⁹¹ We have attended to prescription medication as a confounder. We will adjust for stable antidepressant use (SSRIs and SNRIs) in statistical analyses. Excluding patients taking antidepressants would reduce generalizability.¹⁹²

D.3.3 Study Groups and Interventions.

D.3.3.1 Capnography-Assisted Learned, Monitored Breathing (CALM) Intervention. The 4-week CALM Breathing therapy will consist of eight 1-hour individual treatment sessions over 4 weeks pre-PR (**Tables 1, 3– 4** and section A.1.3). The dose (of 8 sessions plus daily exercises) was primarily guided by participant feedback from our previous CART trial, as well as other breathing therapy trials.^{31,193,194}

D.3.3.2 Fidelity Procedures. To improve the internal validity of study findings, comprehensive fidelity methods will be implemented.¹⁹⁵ These methods will include standardizing interventionist training and supervision protocols; manualizing CALM Breathing; and monitoring and measuring intervention implementation and

receipt. Intervention fidelity is "the extent to which an intervention's core components have been implemented as planned".^{196,p.377} Two interventionists will be trained and certified by [name] to implement CALM Breathing, A 12-hour, standardized training program will be developed consisting of biofeedback demonstrations, case studies, and a mock visit (7 hours); manual assessment techniques (1 hour); and dyspnea, anxiety, behavior change, and MI principles (4 hours).^{197,83} Clinicians will implement CALM Breathing. For certification, [name] will review recordings and written notes of the first three sessions of CALM Breathing and provide detailed feedback.¹⁹⁸ A random selection of 20% of audio-recorded CALM Breathing intervention sessions and written notes (drawn from different therapy phases)¹⁹⁸ will be audited by [name] and discussed during regular supervision meetings to improve interventionists' competence and prevent intervention drift. A fidelity checklist will be used with core CALM Breathing components included. The checklist will use a 0-2 scoring scale and include three domains: session structure, session content, and session tailoring (adapted from another fidelity checklist¹⁹⁹). For coaching, the Motivational Interviewing Treatment Integrity Scale (MITI-4) will be used, which is well validated and includes four global ratings-Cultivating Change Talk, Softening Sustain Talk, Partnership, and Empathy, with a 1–5 scale.²⁰⁰⁻²⁰² CALM Breathing attendance will be tracked closely by the RA. We implemented fidelity monitoring with regular supervision meetings and MITI-4 in our prior CART study.

D.3.3.3 Wait-List Control Group (Study Phase I). After referral to CUIMC's PR program, participants randomized to the Wait-List control group will be put on a PR wait list (usual care).

Table 3. CALM Breathing Sessions.					
Session	Session Plan				
1	 Introduce CALM Breathing; combine initial interview with capnography assessment; manually evaluate respiratory muscle function and assess for lower ribcage paradox (in supine and sitting). Introduce mind-body connection; educate about role of CO₂; discuss link between the breath and emotions. Educate about anxiety, and the cycle of breathing and panic, and related physiology. Discuss overall goals, homework, and target goals; train in RR device and exercise log use. 	40 20			
2–8	 Review homework exercise log and recorded RR data; problem-solve barriers. Implement tailored CALM Breathing exercises (at rest and with low-moderate intensity) and MI. Collaboratively set target behavior goals and discuss home-based breathing exercises. Borg dyspnea score: max. 4.⁷⁷ 	10 40 10			

D.3.3.4 PR Intervention (Standard Care Phase II). CUIMC's PR program will be delivered as part of care as usual (**Table 4**). A wait of approximately 6 weeks for PR is typical at New-York Presbyterian / CUIMC

	Traditional outpatient PR (rolling admission)	CALM Breathing					
Components	Group exercise training (ET) combined with PLB training. ^{77,203}	Individual interoception-based breathing therapy with capnography ^{17,72,77} (non-exercise training ²⁰⁴).					
Home Program	Unmonitored walking exercise 1–2 days/week; no biofeedback monitoring.	Monitored home-based breathing exercises; RR biofeedback; goal setting; exercise logging.					
Coaching	Traditional monitoring and verbal cueing.	Motivational interviewing.					
Personnel	PT	PT, EP, occupational therapist, or nurse.					
Frequency	1-hour sessions, twice per week for 10 weeks.	1-hour sessions, twice per week for 4 weeks.					
Exercises	 ET of muscles of ambulation with exercise equipment, such as treadmill or NuStep (30-min), plus 15-min strengthening exercises; O2 supplementation. No breathing biofeedback. PLB instruction only during exercise training. 	 10 core breathing exercises with ETCO₂ biofeedback in recovery postures at rest and with body movement (gentle stretches and, in later sessions, brief low-moderate intensity PA) Breathing biofeedback (ETCO₂, RR, airflow pattern). 					
Education	Verbal and written information.	• Education on anxiety; COPD Patient Guide. ²⁰⁵					

Note: EP = exercise physiologist. O_2 = oxygen. PLB = pursed lips breathing. PT = physical therapist. RR = respiratory rate.

D.3.4 Study Assessments and Rationale. Study outcome assessments will be implemented at baseline, 4 weeks (±2 weeks), and at a 3-month follow-up (±2 weeks). Baseline characteristics will include demographics, social history, smoking status, hospitalizations in the last 12 months, medications and supplemental oxygen use, BMI, mMRC,¹² living situation, depression²⁰⁶, cognitive deficits,²⁰⁷ and literacy.²⁰⁸ All participants will be administered the Mini-International Neuropsychiatric Interview (MINI)²⁰⁹ by a psychologist to diagnose

psychiatric disorders (anxiety, depression, bipolar disorder, and psychosis). This psychological assessment (not part of standard care) is important to ensure patient eligibility, reduce study risk, and assist with psychological management of participants. All clinical outcome measures are well validated and sensitive to change in COPD or older adults. Medication dosage, intervention doses, and adverse events will be monitored.

D.3.4.1 Outcome Measures.

Feasibility (Aim 1): 1) number of participants recruited within 12 months and reasons for excluding patients; 2) drop-out rate and number of participants lost to follow-up; 3) CALM Breathing treatment session attendance rate and homework adherence; 4) fidelity of CALM Breathing implementation; and (5) facilitation of efficient transition to PR (Phase II). [See Study Record and Statistical Design Plan for more information.]²¹⁰

Acceptability (Aim 2): The acceptability of CALM Breathing will be evaluated based on mixed methods data collected from CALM Breathing attendance, drop-out rate, and satisfaction ratings, and from semi-structured interviews.^{181,211} Overall satisfaction of CALM Breathing and homework breathing exercises will be evaluated using stand-alone single items from FACIT treatment satisfaction instrument.²¹¹ To assess themes related to satisfaction and addressable challenges, we will conduct 20-30-min semi-structured, in-depth interviews using open-ended questions, either in person or by phone, post-CALM Breathing at 4-weeks and at 3-month followup.^{177,212,213} Open-ended questions provide an opportunity for greater understanding of acceptability, satisfaction, and addressable contextual challenges of an intervention, that cannot be elicited from closedended items alone.²¹⁴ Participants will be asked a series of open-ended questions developed from our previous qualitative research.¹⁷⁷ To promote honest answers, as much as possible, interviewer will be blinded to patient social status. Those who dropout will also be interviewed and asked about their experiences with the intervention and reasons for dropping out. The interviewer (research assistant, RA) will receive intensive training from [name] and [name] prior to conducting open-ended interviews. [name] will review the transcripts of initial interviews, critique them, and provide feedback before additional interviews are conducted. Throughout the data collection, [name] will monitor the data guality by randomly reviewing selected subset of interview transcripts, to assess that the interviewer is continuing to maintain neutrality, facilitating spontaneous flow of material with non-directive and unstructured questions, and using appropriate transitions to move the discussion from one topic to another, while eliciting range, depth and personal context in the interview. Interviews will be audio-recorded and transcribed by the RA. Coders will be separate from the interviewer; and will receive intensive training and supervision from [name]. Coders will use coded transcripts. Coded transcripts will be analyzed with Dedoose software.²¹⁵ [See SDP for more details on qualitative analyses.]

Secondary Outcome Measures. *Clinical*: Dyspnea (Chronic Respiratory Disease Questionnaire, CRQ, dyspnea, DMQ-CAT, and modified Borg scale),^{22,216,217} anxiety (GAD-7 and Perceived Stress Scale),^{218,219} 6MWD,²¹⁷ PA,²²⁰ ETCO₂ and RR, QOL^{221,222}, and lung function²²³, and quality of life (PROMIS SF V20 Social Roles, V10 Fatigue, V10 Sleep Disturbance, V20 Physical Function). PR Utilization/Engagement: We will measure PR uptake, treatment initiation, attrition rate, and patient activation (using the unidimensional 13-item Patient Activation Measure^{224,225}), and acceptability of the Massimo Pulse Oximeter (using the "System Usability Scale)".

Mediating (Process) Outcomes: Interoceptive awareness (MAIA scale),^{161,226} AS (ASI-16),^{227,186} dyspnea selfefficacy,²² nasal symptoms (SNOT-20),²²⁸ objective sleep (Actigraphy, Sleep Diary and Nonin Wrist Ox2) and depression (PHQ-9).^{206,229} [See Study Record and SDP.]

D.3.5 Statistical Considerations: Feasibility and Acceptability Success Benchmarks (Aims 1 and 2).

Benchmarks were guided by our prior CART study and other studies.^{200,230}

D.3.5.1 Primary Outcome: Feasibility. We will calculate % and means to determine whether the following success criteria are met; **Table 5**.³²

Table 5. Feasibility Success Criteria.					
1.	40 participants are recruited within 12 months (±3 months).				
2.	≥75% participant retention at 4-week (±2 week) evaluation and 3-month follow-up.				
3.	CALM Breathing session attendance is ≥70%.				
4.	CALM Breathing homework exercise adherence is ≥70% for (5 days/week) using RR device data or exercise log.				
5.	A mean of 1 is achieved on CALM Breathing fidelity checklist items and mean of 4 on MITI-4 scale.				

6. PR intake assessment is scheduled for week 6–10 for ≥75% of all participants.

D.3.5.2 Primary Outcome: Acceptability. Acceptability *a priori* success benchmarks are: $(1) \ge 70\%$ CALM Breathing attendance; (2) CALM Breathing drop-out rate is $\le 10-15\%$; and (3) mean of ≥ 2 "good" satisfaction rating for CALM Breathing treatment overall (item 8 of FACIT; 0–4 scale).²¹¹ [See SDP and Study Record].

D.3.5.3 Secondary Outcomes. Hypothesis testing will not be conducted for secondary outcomes. **D.3.6 Challenges and Alternative Strategies.**

We have carefully examined the number of potential participants and are confident we have the pool of participants needed. Strategies to ensure participant recruitment efficiency and retention have been carefully considered.^{231,232-234} We considered reducing the number of secondary outcomes in our assessment battery but decided it was important to include multiple outcomes for improved rigor.²³⁵ To maintain assessor blinding, the RA (not blinded) will evaluate treatment session and homework adherence outcomes that could reveal intervention group allocation.¹⁹² We will use an iterative process to maximize the likelihood of meeting success benchmarks.²³⁶ We considered offering CO₂ biofeedback for home exercises to increase the dose. However, to keep the home program feasible and easy to carry out, we decided to have participants focus on only one biomarker (RR). If the study findings do not support future clinical trials of CALM Breathing, sub-group analyses will be conducted to illuminate the results (e.g., analyzing feasibility by gender or anxiety level). Revisions might then be made to the study eligibility criteria and/or CALM Breathing intervention.

D.4 Study Milestones.

Table 6. R34 MILESTONES (Months 0-24)		Year 1				Year 2			
· · ·	Q1	Q2	Q3	Q4	Q1	Q2	Q3	Q4	
Aim 1: Evaluate Feasibility of CALM Breathing									
Start-up: Develop recruitment materials (flyer) and intervention manual; Obtain IRB approval; Develop data management and tracking systems; Develop manual of procedures (MOP); Hire	X	Х							
and train study staff; Establish data safety monitoring board.									
Ensure timely execution of agreements	Х	Х	Х	Х	Х	Х	Х	Х	
Screen and recruit 40 study participants				4	12	12	12		40
Complete enrollment/baseline data collection				4	12	12	12		40
Complete 4-week post-intervention data collection				4	12	12	12		40
Complete 3-month follow-up data collection					4	12	12	12	40
Collect primary and secondary endpoints and adverse events				Х	Х	Х	Х	Х	
Complete treatment fidelity audits				Х	Х	Х	Х		
Complete data safety/monitoring reports		Х		Х		Х		Х	
Complete quality control	Х	Х	Х	Х	Х	Х	Х	Х	
Obtain annual IRB renewal					Х			Х	
Conduct statistical analyses				Х	Х	Х	Х	Х	
Submit manuscripts to peer-reviewed journals for dissemination				Х	Х	Х	Х	Х	
Disseminate findings at conferences					Х	Х	Х	Х	
Aim 2: Evaluate Acceptability of CALM Breathing									
Analyze CALM Breathing acceptability				Х	Х	Х	Х	Х	
Disseminate findings at conferences and through publications					Х	Х	Х	Х	
Submit study results to ClinicalTrials.gov								Х	

D.5 Study Organization and Research Team.

At Columbia University Irving Medical Center, CALM Breathing will be led by **[name]**. [name] is an expert in breathing techniques, capnography biofeedback, MI, and behavioral change in COPD. The research team is highly qualified and experienced. At Columbia University, collaborators represent leaders and experts in the fields of rehabilitation (**[name]**), exercise physiology, COPD, and pulmonary clinical trials (**[name], [name], and [name])** and neuropsychology (**[name]**).

NYU is a subcontract site (IRB study #: i20-00751_CR1). To complete our study team, we will collaborate with **[name]** (who will continue to serve as multiple-PI), **[name]** (a specialist in biostatistics), and **[name]** (a specialist in qualitative analyses). 3-month re-evaluations of 4 already randomized participants occurred at NYU. No new participant recruitment or retention procedures will occur at NYU. The procedures that will occur at NYU include: (1) [name] will guide and oversee the implementation of the study remotely from NYU via email and Zoom meetings; (2) [name] will assist with training the RA in qualitative study procedures and supervise the coding of transcribed interview data remotely via email and Zoom meetings –

transcripts will not include any identifiers; and (3) [name] will conduct quantitative data analyses for the study using a coded dataset and work closely with the PIs via Zoom and email.

D.6 Future, Large-Scale Clinical Trial.

With achievement of clearly established success benchmarks and milestones, we will demonstrate readiness to proceed to implement a large, adequately powered Phase III efficacy trial.²³⁷ The primary hypotheses for the future clinical trial will be that CRQ-dyspnea and 6MWD mean differences will be greater (≥ minimal important differences, MID) in CALM Breathing compared with waitlist control group at 4 weeks. Two primary outcomes of symptom impact are indicated, which have been rated by stakeholders as important.²³⁸ Our Phase III study will have a 12-month follow-up period. We will also explore mechanisms of CALM Breathing.

References

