- D. Feasibility Aim 1. We will calculate % and means to determine whether the following success criteria are met: (1) 40 participants are recruited within 12 months (±3 months); (2) ≥75% participant retention at 4-week (±2 week) evaluation and 3-month follow-up; (3) CALM Breathing session attendance is ≥70%; (4) CALM Breathing homework exercise adherence is ≥70% for (5 days/week) using RR device data and exercise log; (5) A mean of 1 is achieved on CALM Breathing fidelity checklist items and mean of 4 on MITI-4 scale; and (6) PR intake assessment is scheduled for week 6 –10 for ≥75% of all participants. Cutoffs are based on our previous CATCH study and other studies.
- E. Acceptability Aim 2. The acceptability of the CALM Breathing therapy will be evaluated based on mixed methods data collected from CALM Breathing attendance, drop-out, and satisfaction ratings, and from semi-structured interviews.^{5,6} Acceptability of CALM Breathing will be determined by: (1) ≥70% CALM Breathing attendance; (2) CALM Breathing drop-out rate of ≤10–15%; and (3) mean of ≥2 "good" satisfaction rating for CALM Breathing treatment overall (item 8 of FACIT; (0–4 scale).⁶ Single FACIT Treatment Satisfaction items (6 and 8) ask: (1) "Would you recommend this treatment to others with your illness?" (with 0–2 rating scale, 0 = "No", 1 = "Maybe", 2 = "Yes"); and (2) "How do you rate this treatment [CALM Breathing] overall?" (with 0–4 rating scale, 0 = "poor" and 4 = "excellent"). We will also ask, "How do you rate the CALM Breathing home exercises overall?" (and use the same FACIT 0–4 rating scale).

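### The pilot is meant to test whether blinding is achievable, but no listed outcome or success criterion records whether the assessor stayed blind

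*Protocol*

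**What the plan says.** Protocol D.3.1.2 sets out eight things whose feasibility the pilot is to test. The item on assessment procedures ends with "testing that target timelines and blinding are achievable". That item does not say whose blinding, but Protocol D.3.6 does: "To maintain assessor blinding, the RA (not blinded) will evaluate treatment session and homework adherence outcomes that could reveal intervention group allocation".

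The Aim 1 outcomes in Protocol D.3.4.1 start with "number of participants recruited within 12 months and reasons for excluding patients" and go on to drop-out and loss to follow-up, attendance and homework, fidelity, and transition to pulmonary rehabilitation (PR). Protocol Table 5 and SAP section D give the same six success criteria. SAP section D introduces them with "We will calculate % and means to determine whether the following success criteria are met", and the last one in Table 5 is "PR intake assessment is scheduled for week 6–10 for ≥75% of all participants". Protocol D.6 says that, once the benchmarks and milestones are achieved, "we will demonstrate readiness to proceed to implement a large, adequately powered Phase III efficacy trial".

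**The concern.** The lists that decide whether the pilot succeeded do not carry this purpose through to a measurement. Giving adherence data to the unblinded research assistant is a precaution. It closes one route by which the assessor could learn the allocation, but it does not show whether blinding held, and it does not cover a participant simply telling the assessor. One arm has had eight individual biofeedback sessions and home practice with a device, while the other has waited, so participants have something to disclose.

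Protocol D.6 names CRQ-dyspnea and six-minute walk distance as the Phase III primary outcomes. The walk test is administered by staff and depends on effort, so whether its assessor can be kept blind is a fair question for a pilot to settle. If disclosure is not recorded at the visit, no later analysis can recover it.

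**Working it through.** The documents state no figure for blinding, so there is none to reproduce. The check compares the stated purpose with each list of outcomes and criteria.

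1. **Purpose.** Protocol D.3.1.2, assessment-procedures item: timelines and blinding are to be shown achievable.
2. **Whose blinding.** The outcome assessor's. This is inferred from the item's subject and from D.3.6.
3. **Items that measure it.**
   - Feasibility outcomes (Protocol D.3.4.1): 0 of 5.
   - Feasibility success criteria (Protocol Table 5; SAP D), covering recruitment, retention, attendance, homework, fidelity and PR intake timing: 0 of 6.
   - Acceptability benchmarks (Protocol D.3.5.2; SAP E), covering attendance, drop-out and satisfaction: 0 of 3.
   - Secondary, utilization and mediating outcomes (Protocol D.3.4.1; SAP G to I) and milestones (Protocol Table 6): none.
4. **Other mentions.** The SAP does not mention blinding. The remaining mention in the visible protocol is in D.3.4.1, where the interviewer is masked to social status, which is not treatment allocation.
5. **The other half of the clause.** Timelines are partly covered, by the visit window in criterion 2 and the intake window in criterion 6. Blinding has no counterpart.

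**What a simple record could show.** Inputs are 40 participants randomised 1:1 (SAP, Study Design), so 40/2 = 20 per arm, and the 75% retention benchmark (Table 5), so 0.75 × 40 = 30 assessed at a visit. The proportion unblinded is not given anywhere. One half is assumed because it gives the widest interval. At a proportion of 0.5 the Wilson 95% interval is 0.5 ± z / (2√(n + z²)), with z = 1.96 and z² = 3.84.

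- n = 30: 1.96 / (2√33.84) = 1.96 / 11.63 = 0.168, giving 33% to 67%.
- n = 20 (one arm, no loss): 1.96 / (2√23.84) = 1.96 / 9.77 = 0.201, giving 30% to 70%.

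At the other end, with no unblinding observed, the upper Wilson limit is z² / (n + z²). That is 3.84/33.84 = 11% for n = 30 and 3.84/23.84 = 16% for n = 20.

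**The case against.** **Unseen text.** The copy reviewed lacks the protocol text between the D.1 heading and D.3.1.1. D.3.4.1 refers to a Study Record, and Table 6 mentions a manual of procedures; neither was available. A blinding check could be described in any of these. This stands. A reader might infer that the trial will hold no data at all on blinding, or that the D.3.6 precaution is its only safeguard. The documents support neither; they support only that the listed outcomes and criteria contain no such measure.

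**A small part of the purpose.** Blinding is half of one clause among eight purposes. Other purposes, such as the screening instruments, randomisation, assessment time and burden ratings, also lack a criterion, and the protocol never promises a benchmark for each. This stands too: it is an unmeasured purpose, not a contradiction. It is still worth fixing, because the information is lost if not recorded at the visit.

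**Little at stake in the pilot.** Attendance, retention, homework, fidelity and satisfaction do not depend on a blinded assessor, and secondary outcomes undergo no hypothesis testing (Protocol D.3.5.3; SAP J). CRQ-dyspnea is patient-reported (SAP G), so an assessor check would not address bias in it, and the walk test follows a standard procedure. All of this stands and confines the point mainly to walk distance in a later trial.

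**Likelihood of disclosure.** A reader might infer from the contrast between arms that assessors will probably be unblinded. That is a reasonable expectation, but the documents give no rate.

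**An arm-guess test.** It is tempting to say that 40 guesses would expose failed blinding, since 26 or more correct has a chance probability of 4%. But that assumes no loss and no don't-know answers. The chance of reaching 26 is 57% if true accuracy is 65%, and 81% if it is 70%. A guess can also reflect perceived benefit rather than disclosure.

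**Conclusion.** The point holds in a limited form. The protocol names achievable blinding as something the pilot tests, yet 0 of 5 feasibility outcomes, 0 of 6 feasibility criteria and 0 of 3 acceptability benchmarks measure it. All of them could be met, and Phase III readiness stated, with no planned result on this purpose. The conclusion rests on reading blinding as assessor blinding, which D.3.6 supports well, and on the visible lists being complete.

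Severity is minor, and this is a cheap improvement. The pilot's feasibility and acceptability conclusions are not biased by the gap. Nor do the documents support making Phase III readiness conditional on a blinding result: SAP section J expressly declines firm go/no-go criteria, so reporting the figure is enough.

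**What to change.** At the 4-week and 3-month visits, have the blinded assessor record in REDCap (i) whether the participant's allocation was disclosed or otherwise became known, and (ii) if so, whether this was before or after the walk test.

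Add one descriptive feasibility result to SAP section D: the number and percentage of assessments with unblinding at each visit, overall and by arm, with 95% CI. Report it beside the existing criteria, without a pass/fail threshold. Giving the two visits separately avoids treating repeat assessments of one participant as independent.

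An assessor's guess of arm, with a don't-know option, may be added but should be interpreted cautiously because it can reflect perceived benefit.

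The cost is one or two extra items per visit and one line in the SAP, with no new visit. The downside is that an unfavourable figure might have to be reported.

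### The PR-timing benchmark (intake in week 6–10, arms pooled, week 0 unstated) cannot show whether CALM shortens or lengthens the wait for PR

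*Protocol*

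**What the plan says.** Both documents give the same rule. Protocol D.3.5.1, Table 5, criterion 6 reads "PR intake assessment is scheduled for week 6–10 for ≥75% of all participants", and SAP section D, item 6 reads "PR intake assessment is scheduled for week 6 –10 for ≥75% of all participants". Neither says which event is week 0. The denominator is both arms together, and no comparison between arms is attached.

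The matching feasibility outcome in Protocol D.3.4.1 is "facilitation of efficient transition to PR (Phase II"). Protocol D.3.1.2, item 5 gives the purpose as "facilitating timely PR intake assessment initiation (to limit wait").

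The usual wait appears twice. Protocol D.3.3.4 says "A wait of approximately 6 weeks for PR is typical at New-York Presbyterian / CUIMC", with no start or end point. Protocol D.3.1.1 says "PR intake evaluations are typically scheduled 6 weeks in advance of implementation" and concludes: "Therefore, 4-week CALM Breathing could fit seamlessly into PR programs and not delay standard of care".

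On recruitment, Protocol D.3.2 begins with the "outpatient PR program patient referral list" and then adds pulmonology and primary care departments, a second hospital and a recruitment platform. People on the referral list were referred before they entered the study.

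The other PR outcomes in SAP section H are uptake, treatment initiation, attrition, share of sessions completed and patient activation. None is a time.

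**The concern.** The Wait-List design is defended on the ground that four weeks of CALM fit inside the usual wait, and one feasibility purpose is to keep that wait short. A reader will look to criterion 6 for evidence on both, because nothing else planned measures time to PR.

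The criterion is poorly shaped for that use. A pooled percentage can hide a gap between arms. An upper edge beyond the usual wait lets late intakes count as success. A lower edge makes early intakes count against the trial, and early and late intakes enter the result as the same kind of failure. Without a stated week 0, the percentage cannot be converted into weeks waited. At stake is whether the pilot can support any statement that CALM leaves standard care undelayed. Protocol D.6 ties readiness for the larger trial to meeting the benchmarks.

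**Working it through.** The documents give no calculation behind this criterion, so there is no planned figure to reproduce. What follows is arithmetic on the window.

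**Inputs.** N = 40 and 1:1 allocation (SAP, Study Design), taken as 20 per arm. Threshold 75% and window week 6 to 10 (Table 5). Usual wait about 6 weeks (Protocol D.3.3.4), read here as the wait to intake. L = weeks from PR referral to study baseline; the documents do not give L, so 0, 1 and 2 are shown as assumptions.

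**Threshold.** 0.75 × 40 = 30, so up to 10 participants may fall outside the window.

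**Passing with a gap between arms.**
- CALM all at week 10, Wait-List all at week 6: (20 + 20)/40 = 100%, with CALM 10 − 6 = 4 weeks later.
- Wait-List 20/20 and CALM 10/20 in the window: 30/40 = 75%. This passes although half the CALM arm missed the window.

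**Effect of week 0.** If week 0 is baseline, an intake 6 weeks after referral falls at study week 6 − L. An intake at study week 10 is 10 + L weeks after referral, an excess of 4 + L.

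| L (assumed) | Study week of a 6-week intake | In window? | Week 10, counted from referral | Excess over 6 |
|---|---|---|---|---|
| 0 | 6 | yes | 10 | 4 |
| 1 | 5 | no | 11 | 5 |
| 2 | 4 | no | 12 | 6 |

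The L = 0 row also describes a week 0 set at referral, so 4 weeks is the minimum excess under either anchor.

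**Illustration: sensitivity to delay in the CALM arm.** Assume normally distributed intake times with SD 1 week and a Wait-List mean at week 7 (neither is in the documents). The chance of at least 30/40 in the window is 0.955 with no CALM delay, 0.999 with a 1-week delay and 0.955 with a 2-week delay. It falls to 0.165 at 3 weeks and below 0.001 at 4. A 2-week delay is therefore indistinguishable from none, and a 1-week delay raises the pass rate.

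**Illustration: the lower edge.** Assume all 40 wait a normally distributed time with mean 6 weeks from referral, and L = 0. With exact edges, about half fall before week 6, and the chance of passing is 0.0011 or less for SD 0.5, 1 or 2. Widening the edges to 5.5 and 10.5 gives 0.96, 0.27 and 0.02 respectively. With a baseline anchor and L = 1 or 2, the chance is about zero in every case. These results depend on the assumed SD, L and rounding rule.

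**The case against.** Several objections have force.

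- **Anchor.** A reader might infer that the weeks certainly run from study baseline. Neither document says so for this criterion. The support is indirect: the SAP labels baseline as week 0 for spirometry and actigraphy, and criterion 2 in the same table uses study weeks. Part of the protocol before D.3.1.1 was not available and may define the timeline.
- **Failure under normal PR timing.** A reader might infer that the benchmark would read 0% if PR simply kept its usual schedule. That needs a baseline anchor, at least one week between referral and baseline for everyone, and waits of exactly 6 weeks from referral. The documents give no such lag, some participants come from outside the referral list, and Protocol D.3.3.3 can be read as starting the wait at randomization. On that last reading a 6-week wait lands on week 6 and passes.
- **Attribution.** All 40 intakes could be 4 weeks late and score 100%, but a delay shared by both arms could not be attributed to CALM. The problem lies in pooling.
- **The 6 weeks.** Protocol D.3.1.1 can be read as the time from intake to the start of PR. The intake window would then not be comparable with it.
- **Lower edge.** CALM is meant to come before PR, and the 4-week assessment (±2 weeks) closes at week 6. This is a plausible reason for the edge, though the documents do not state it.
- **Weight.** SAP section J says the criteria are not firm stop-or-go rules, and intakes after week 10 do count against the benchmark, so it is not blind to every delay.

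These points limit the claim. They do not remove the pooling, the missing week 0 or the absence of any other timing measure.

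**Conclusion.** The concern holds in a limited form. Criterion 6 can be met at 100% with CALM intakes 4 weeks later than Wait-List intakes, and at 75% with half the CALM arm outside the window. It counts early intake as failure, against its own stated purpose. These three results need only the window, the pooling and 20 per arm. The excess of at least 4 weeks over the usual wait further assumes that the 6 weeks run to intake; the 4 + L form assumes a baseline anchor.

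The documents do not establish that the clock starts at baseline, that normally scheduled PR would fail the benchmark, or that CALM delays PR. They also do not show that the lower edge is a mistake. The finding is that the planned measure could not settle these questions. This is a cheap improvement that changes what the pilot can conclude; it takes no position on when PR should start.

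**What to change.** 1. Reconcile Protocol D.3.1.1, D.3.3.4 and Table 5 with SAP section D, item 6: state what week 0 is, and what the 6-week wait runs from and to.
2. Record the PR referral date. For participants recruited outside the referral list, use the date of the study-prompted referral.
3. Report referral-to-intake time by arm (median and range) beside the usual wait that the protocol cites. Base any statement that CALM does not delay standard care on that comparison.
4. Report intakes before week 6 separately from those after week 10.
5. Keep the week 6–10 percentage as a measure of study scheduling.

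The cost is one extra date field and edits to two documents. The downside is a result that may look less favourable than the pooled percentage. With about 20 per arm the comparison by arm will be descriptive, in line with the rest of the plan.
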